## Appendix 1: Scales

### 1. The thrombolysis in cerebral infarction (TICI) grading system

The TICI system was described in 2003 by Higashida et al. as a tool for determining the response of thrombolytic therapy for acute ischaemic stroke. In neurointerventional radiology it is commonly used for patients post-endovascular revascularisation. Like most therapy response grading systems, it predicts prognosis.

The original description was based on the angiographic appearances of the treated occluded vessel and the distal branches:

- Grade 0: no perfusion
- Grade 1: penetration with minimal perfusion
- Grade 2: partial perfusion
  - Grade 2a: only partial filling (less than two-thirds) of the entire vascular territory is visualised
  - Grade 2b: complete filling of all of the expected vascular territory is visualised but the filling is slower than normal
- Grade 3: complete perfusion

A consensus paper from three collaborative groups published in *Stroke* in 2013 recommended a modified scale, and a change of name to the modified Treatment in Cerebral Infarction (mTICI), to better reflect the increased use of endovascular therapies. Essentially, there was simplification of the TICI 2 component to less than half of the target vascular territory (mTICI 2a) or more than half (mTICI 2b).

#### Classification

- grade 0: no perfusion
- grade 1: antegrade reperfusion past the initial occlusion, but limited distal branch filling with little or slow distal reperfusion
- grade 2
  - grade 2a: antegrade reperfusion of less than half of the occluded target artery previously ischaemic territory (e.g. in one major division of the middle cerebral artery (MCA) and its territory)
  - grade 2b: antegrade reperfusion of more than half of the previously occluded target artery ischaemic territory (e.g. in two major divisions of the MCA and their territories)
- grade 3: complete antegrade reperfusion of the previously occluded target artery ischaemic territory, with absence of visualised occlusion in all distal branches

The **expanded treatment in cerebral infarction (eTICI) score** is a further modification of the mTICI and TICI scales, published by the HERMES investigators in 2019. Using mRS shift analysis as the outcome measure, the investigators found a significant difference in outcomes for patients with partial recanalisation after EVT between those with reperfusion of 50-66%, 67-89% and 90-90%, in addition to those previously defined by mTICI.

#### Classification

- grade 0: no perfusion noted (0% reperfusion)
- grade 1: reduction in thrombus but without any resultant filling of distal arterial branches
- grade 2
  - grade 2a: reperfusion of 1-49% of the territory

- grade 2b50: reperfusion of 50–66% of the territory
- grade 2b67: reperfusion of 67–89% of the territory
- grade 2c: extensive reperfusion of 90–99% of the territory
- grade 3: complete or full reperfusion (100% reperfusion)

## 2. Heidelberg bleeding classification

### Class 1: haemorrhagic transformation of infarcted brain tissue

1a: HT1: scattered small petechiae, no mass effect

1b: HT2: confluent petechiae, no mass effect

1c: PT1: haematoma within infarcted tissue, occupying <30%, no substantive mass effect:

### Class 2: intracerebral haemorrhage within and beyond infarcted tissue

PH2: haematoma occupying ≥30% of the infarcted tissue with obvious mass effect

### Class 3: intracerebral haemorrhage outside the infarcted brain tissue or intracranial-extracranial haemorrhage

3a: parenchymal haematoma remote from infarcted tissue

3b: intraventricular haemorrhage

3c: subarachnoid haemorrhage

3d: subdural haemorrhage

Symptomatic haemorrhages are considered definite if any intracranial haemorrhage is the dominant brain pathology on imaging causal for deterioration. However, in some cases, the causality is not certain because the ischaemic infarct may have contributed to the deterioration, so the following classification is applied for reporting of trials:

Symptomatic

probable relatedness: class 2 (PH2) haemorrhage

Asymptomatic

Possibly relatedness: class 1b (HT2), 1c (PH1) and 3 haemorrhages

Unlikely relatedness: class 1a (HT1) haemorrhage

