6.8. Study Outcomes

Primary outcome

Functional outcomes defined as a shift (improvement) in scores on the mRS at 90 days (3 months). The mRS is a widely used instrument for grading the impact of stroke treatments, with scaling of: 0 = no symptoms at all; 1 = no significant disability despite symptoms, but able to carry out all usual duties and activities; 2 = slight disability, unable to carry out all

previous activities but able to look after own affairs without assistance; 3 = moderate disability requiring some help, but able to walk without assistance; 4 = moderate-severe disability, unable to walk without assistance and unable to attend to own bodily needs without assistance; 5 = severe disability, bedridden incontinent, and requiring constant nursing care and attention; 6 = dead.

Secondary outcomes are:

- 1) ICH: a) sICH, based on National Institutes of Neurological Diseases and Stroke (NINDS) criteria of brain imaging (or necropsy) confirmed ICH with ≥ 1 points deterioration in NIHSS score or death within 36 hours from baseline; b) sICH, defined by Safe Implementation of Thrombolysis in Stroke-Monitoring Study (SITS-MOST) criteria, as large ('type II') parenchymal ICH with ≥ 4 points decline in NIHSS score or death within 36 hours from baseline; c) sICH, defined by the new Heidelberg Bleeding Classification (HBC) criteria; d) ICH of any type in brain imaging ≤ 7 days of treatment; e) any symptomatic ICH (sICH) after MT within 90 days. ICH will be assessed by CT imaging and adjudicated centrally.³³
- 2) Imaging endpoints: a) infarct size growth assessed by MRI at 48 hours; b) edema volume assessed by CT at Day 7.
- 3) Death or dependency measured by NIHSS at 7 days;
- 4) The followings at 90 days: Death or major disability (mRS 3-6); separately on death and disability (mRS 3-5); health-related quality of life (HRQoL) using EQ-5D; duration of hospitalisation; residence and hospital service cost.

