### 2.4.2 Secondary outcomes

- Intracerebral haemorrhage (ICH), assessed by CT imaging and adjudicated centrally according to five possible definitions:
  - a) symptomatic ICH (sICH), based on National Institutes of Neurological Diseases and Stroke (NINDS) criteria of brain imaging (or necropsy) confirmed ICH with  $\geq$ 1 points deterioration in NIHSS score or death within 36 hours from baseline
  - b) sICH, defined by Safe Implementation of Thrombolysis in Stroke-Monitoring Study (SITS-MOST) criteria, as large ('type II') parenchymal ICH with  $\geq$ 4 points decline in NIHSS score or death within 36 hours from baseline
  - c) sICH, defined by the new Heidelberg Bleeding Classification (HBC) criteria, the details of which are outlined in Appendix 1. *This will be the primary safety measure.*
  - d) ICH of any type in brain imaging  $\leq$ 7 days of treatment

- e) any sICH after EVT within 90 days
- Imaging outcomes
  - a) infarct size assessed by any form of brain imaging (MRI or CT) at 48±24 hours
  - b) oedema size assessed by MRI or by CT during days 2-7
- Death or dependency, measured by NIHSS at 7 days
- The followings at 90 days:
  - Death or major disability (mRS 0-2 vs mRS 3-6)
  - Death and disability as separate categories (mRS 0-2 vs mRS 3-5 vs mRS 6)
  - Health-related quality of life (HRQoL) using EuroQoL EQ-5D-3L scale
  - Duration of hospitalisation
  - Residence
  - Hospital service cost (part of separate health economic analysis)

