### 3.1 Statistical principles

#### 3.1.1 Level of statistical significance

The study includes two formal interim analysis after approximately one third and two thirds of patients have completed their 90-day follow-up, using the Haybittle-Peto stopping rule (3 standard-deviations) for efficacy. To account for these two interim analyses, the significance threshold will be set at 4.82% for the final analysis. In case the trial is stopped early, the significance threshold will be adjusted accordingly, to account for the amount of 'alpha' spent.

Final analysis of the primary outcome, including sensitivity analyses, will all be conducted using a two-sided significance level of 4.82%.

For the 7 secondary clinical outcomes ([1] death or dependency at 7 days, and the following at 90 days: [2] death or major disability, [3] death, [4] disability, [5] HRQoL, [6] Duration of hospitalisation and [7] residence ), the family-wise error rate will be controlled by applying a sequential Holm-Sidak correction. Briefly, the approach consists of ordering all p values from smallest to largest, and then comparing them to an adjusted level of significance calculated as  $1-(1-0.05)^{1/C}$ , where C indicates the number of comparisons that remain. In the case of seven 7 secondary outcomes, the smallest p value would be compared to  $1-(1-0.05)^{1/7}$ , the second p value to  $1-(1-0.05)^{1/6}$ , and so on, with the last one being compared to  $1-(1-0.05)$  (i.e. 0.05). The sequential testing procedure stops as soon as a p value fails to reach the corrected significance level. This will apply only to the primary analysis of the secondary outcomes (i.e. not to the adjusted models). For HRQoL, it will only apply to the analysis of the overall score. For ICH outcomes, the Heidelberg Bleeding Classification (HBC) criteria will be considered the primary measure with other definitions considered supportive. No multiplicity adjustment will be applied to the two imaging outcomes (infarct and oedema size) which are considered intermediary mechanistic outcomes.

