### Relatedness to intervention is further specified following reperfusion therapy:

Definite: observed procedural complication

Probable: treatment within 24 hours and class 1c or 2 hemorrhage (PH) (symptomatic or asymptomatic)

Possible: treatment within 24 hours and class 1a or 1b haemorrhage (HI) (symptomatic or asymptomatic)

Unrelated: no intervention in the 24 hours prior to haemorrhage detection

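### SAP Appendix 1, the only operational definition of the primary safety measure (Heidelberg sICH), contains two incompatible rules for what is symptomatic and no deterioration threshold, time window or list of counted categories

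*SAP*

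**What the plan says.** Protocol 6.8 gives this outcome by name only: "sICH, defined by the new Heidelberg Bleeding Classification (HBC) criteria". SAP 2.4.2(c) repeats the name, adds "the details of which are outlined in Appendix 1", and then says "This will be the primary safety measure". SAP 3.1.1 confirms the ranking: for ICH outcomes the Heidelberg "criteria will be considered the primary measure with other definitions considered supportive". SAP 3.8.2 analyses it as a yes/no event per subject, and it is the first row of Table 14.

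SAP Appendix 1, item 2, then has three relevant pieces:

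- A sentence based on deterioration: "Symptomatic haemorrhages are considered definite if any intracranial haemorrhage is the dominant brain pathology on imaging causal for deterioration".
- A list for cases in which "the causality is not certain because the ischaemic infarct may have contributed to the deterioration". Under the heading Symptomatic it has class 2 (PH2), graded probable. Under the heading Asymptomatic it has "Possibly relatedness: class 1b (HT2), 1c (PH1) and 3 haemorrhages", followed by class 1a, graded unlikely. No entry carries a clinical criterion.
- A block on relatedness to the intervention, with entries such as "Probable: treatment within 24 hours and class 1c or 2 hemorrhage (PH) (symptomatic or asymptomatic". A parallel entry treats classes 1a and 1b in the same way.

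The NINDS and SITS-MOST definitions in SAP 2.4.2(a) and (b) state an NIHSS change (at least 1 and at least 4 points) or death, within 36 hours. Neither 2.4.2(c) nor Appendix 1 gives a threshold or a window for Heidelberg sICH.

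**The concern.** A binary safety endpoint needs one rule that turns a scan and a clinical course into yes or no. Appendix 1 is the only place in the two documents where that rule could be found, and it mixes two attributes: whether the patient got worse, and how likely it is that the bleed was the cause. Because the list is what Appendix 1 says trials use for reporting, a programmer or adjudicator could reasonably treat its headings as the event rule. Symptomatic status would then follow from anatomical class alone.

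At stake is the count in the first row of Table 14, in an open-label trial whose hypothesis (Protocol 4.2.3) and secondary aims (Protocol 5.2) include less intracranial bleeding. An event rule that is still open when the data are unblinded leaves room for a choice made with knowledge of the results.

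**Working it through.** No arithmetic can be reproduced, since the documents give no sICH rate or power for this endpoint. The check is to run the same patients through each piece of Appendix 1.

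| Patient | Sentence on definite cases | List headings used as the event rule | Relatedness block |
|---|---|---|---|
| Class 2, bleed is the dominant cause of deterioration | symptomatic | Symptomatic | either possible |
| Class 3, bleed is the dominant cause of deterioration | symptomatic | Asymptomatic | class 3 not listed |
| Class 2, no deterioration | not symptomatic | Symptomatic | either possible |
| Class 1b or 1c, deteriorated, cause uncertain | not definite, passes to the list | Asymptomatic | either possible |

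**Reading 1: the list headings are the event rule for all patients.** Rows 2 and 3 are coded in opposite ways by the sentence and the list. For the size, let D2 be patients with PH2 and deterioration, D13 patients with only class 1 or 3 bleeds and deterioration, and S2 patients with PH2 and no deterioration. For simplicity, take each deterioration as attributable to the bleed. Then:

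- a deterioration rule for any class counts D2 + D13;
- the list counts D2 + S2;
- the difference, list minus deterioration rule, is S2 − D13.

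Neither S2 nor D13 can be obtained from the documents, so neither the size nor the sign of the difference is known.

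**Reading 2: the list applies only where causality is uncertain.** Row 2 is then settled by the sentence as symptomatic, and row 3 never reaches the list. Row 4 remains. By the lead-in this patient has deteriorated, yet the heading says Asymptomatic. So the list contradicts itself even on the milder reading.

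**Which categories count.** On either reading, Appendix 1 grades cases as definite, probable, possible or unlikely, but no section says which of these make up the event in Table 14. At least three nested counts are open: definite only; definite plus probable; definite plus probable plus possible. Row 4 is an event only under the third.

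**Consistency with the relatedness block.** If class fixed symptomatic status, classes 1a, 1b, 1c and 2 could not each be symptomatic or asymptomatic. The block therefore rules out the headings as a class-based definition.

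**The case against.** The strongest defence is that the list must be read with its lead-in. The first sentence is a deterioration rule for any intracranial haemorrhage, so a patient made comatose by a subarachnoid or remote parenchymal bleed is definite symptomatic. A silent PH2 does not meet the lead-in. The list entries are worded as grades of relatedness, and the next block treats symptoms and class as separate. On this view two headings are misplaced and nobody meant to redefine sICH as PH2 on imaging. Bleeds are adjudicated centrally, the Clinical Endpoints Committee works to criteria fixed in advance (Protocol 13.5), and the SAP cites the published classification. Five ICH definitions are reported. The NINDS one has no class restriction, so symptomatic class 1 and 3 bleeds within its window stay visible. ICH lies outside the Holm-Sidak family, and the primary efficacy analysis is untouched.

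Much of this stands. A reader might infer that the primary safety measure ignores deterioration, or that no class 1 or class 3 bleed could ever count. The documents do not support either, because the sentence on definite cases keeps a deterioration rule for every class. Nor do they support a percentage of lost events, or show that adjudicators lacked a threshold in papers outside these two documents.

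The defence does not remove the defect. Misplaced headings still label deteriorated patients as asymptomatic, and nothing else in either document states the event rule. Supportive definitions do not repair the measure ranked above them.

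**Conclusion.** The point holds as an internal contradiction and an incomplete endpoint definition. The primary safety count cannot be reproduced from the SAP as written, because the outcome depends on which rule in Appendix 1 is applied and which relatedness categories are counted. Leaving out deteriorated patients with class 1 or 3 bleeds, and counting a PH2 without deterioration, are both conditional on the list being used as the event rule. The size is unknown.

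This rests on two assumptions: that no other document available to the trial team resolves the rule, and that the two headings stand in the laid-out SAP where they stand in the text. The entries that name only classes, and the missing threshold and window, do not depend on layout. The point deserves correction before unblinding because it concerns the measure that the SAP itself calls primary for safety.

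**What to change.** In SAP Appendix 1, remove the headings Symptomatic and Asymptomatic from the class list and keep probable, possible and unlikely purely as grades of relatedness. Then state one event rule for Heidelberg sICH, fixed before unblinding:

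- a new intracranial haemorrhage of any class, with neurological deterioration, adjudicated blind to allocation;
- the deterioration criterion, the reference NIHSS assessment and the time window, as the NINDS and SITS-MOST definitions already have;
- the relatedness categories that count as the event in Table 14.

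The sponsor should take the threshold and window from the Heidelberg criteria it cites. The 4-point change in the SITS-MOST definition should not be carried over by default, as the documents do not establish it for Heidelberg. Tabulate anatomical class separately. Reconcile the list with the relatedness block, and correct the label drift in the same item (class 1c is PT1 in one place and PH1 in another; HT in one block becomes HI in the next).

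The cost is wording in the SAP and on the adjudication form, with no new procedure. One limit should be acknowledged. NIHSS is scheduled after MT, at 24 hours and at Day 7 or discharge (Protocol 6.10.4 and 6.10.5), so a deterioration between visits may have no score. The NINDS and SITS-MOST definitions share that limit, and the rule should say what evidence is accepted in its place.

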### Relatedness to intervention is further specified following reperfusion therapy:

Definite: observed procedural complication

Probable: treatment within 24 hours and class 1c or 2 hemorrhage (PH) (symptomatic or asymptomatic)

Possible: treatment within 24 hours and class 1a or 1b haemorrhage (HI) (symptomatic or asymptomatic)

Unrelated: no intervention in the 24 hours prior to haemorrhage detection

## Appendix 2: Proposed Tables and figures

### 4.1 Tables

**Table 1. Baseline characteristics**

	Intensive BP lowering (N = )	Guideline-recommended BP lowering (N = )	Total (N = )
Age (years)	xxx	xxx	xxx
Mean (SD)	xxx.x (xxx.x)	xxx.x (xxx.x)	xxx.x (xxx.x)
Median (Q1; Q3)	xxx (xxx; xxx)	xxx (xxx; xxx)	xxx (xxx; xxx)
min max	xxx to xxx	xxx to xxx	xxx to xxx
Sex	xxx	xxx	xxx
Male	xxx xx.x%	xxx xx.x%	xxx xx.x%
Female	xxx xx.x%	xxx xx.x%	xxx xx.x%
Ethnicity	xxx	xxx	xxx
Chinese	xxx xx.x%	xxx xx.x%	xxx xx.x%
Caucasian/European	xxx xx.x%	xxx xx.x%	xxx xx.x%
Other	xxx xx.x%	xxx xx.x%	xxx xx.x%
Systolic Blood Pressure (mmHg) on arrival	xxx	xxx	xxx
Mean (SD)	xxx.x (xxx.x)	xxx.x (xxx.x)	xxx.x (xxx.x)
Median (Q1; Q3)	xxx (xxx; xxx)	xxx (xxx; xxx)	xxx (xxx; xxx)
min max	xxx to xxx	xxx to xxx	xxx to xxx
Diastolic Blood Pressure (mmHg) on arrival	xxx	xxx	xxx
Mean (SD)	xxx.x (xxx.x)	xxx.x (xxx.x)	xxx.x (xxx.x)
Median (Q1; Q3)	xxx (xxx; xxx)	xxx (xxx; xxx)	xxx (xxx; xxx)
min max	xxx to xxx	xxx to xxx	xxx to xxx
Heart Rate (bpm)	xxx	xxx	xxx
Mean (SD)	xxx.x (xxx.x)	xxx.x (xxx.x)	xxx.x (xxx.x)
Median (Q1; Q3)	xxx (xxx; xxx)	xxx (xxx; xxx)	xxx (xxx; xxx)
min max	xxx to xxx	xxx to xxx	xxx to xxx
Blood Glucose (mmol/L)	xxx	xxx	xxx
Mean (SD)	xxx.x (xxx.x)	xxx.x (xxx.x)	xxx.x (xxx.x)

	Intensive BP lowering (N = )	Guideline-recommended BP lowering (N = )	Total (N = )
Median (Q1; Q3)	xxx (xxx; xxx)	xxx (xxx; xxx)	xxx (xxx; xxx)
min max	xxx to xxx	xxx to xxx	xxx to xxx
Pre-stroke modified Rankin scale	xxx	xxx	xxx
0 - no symptoms	xxx xx.x%	xxx xx.x%	xxx xx.x%
1 - no significant disability (with symptoms)	xxx xx.x%	xxx xx.x%	xxx xx.x%
2 - slight disability (but independent in daily activities)	xxx xx.x%	xxx xx.x%	xxx xx.x%
3 - moderate disability (requiring some help from another person for daily activities)	xxx xx.x%	xxx xx.x%	xxx xx.x%
4 - moderate severe disability (requiring regular help from another person)	xxx xx.x%	xxx xx.x%	xxx xx.x%
5 - severe disability (bed bound, totally dependent)	xxx xx.x%	xxx xx.x%	xxx xx.x%
NIHSS Score on arrival	xxx	xxx	xxx
Mean (SD)	xxx.x (xxx.x)	xxx.x (xxx.x)	xxx.x (xxx.x)
Median (Q1; Q3)	xxx (xxx; xxx)	xxx (xxx; xxx)	xxx (xxx; xxx)
min max	xxx to xxx	xxx to xxx	xxx to xxx
GCS Score on arrival	xxx	xxx	xxx
Mean (SD)	xxx.x (xxx.x)	xxx.x (xxx.x)	xxx.x (xxx.x)
Median (Q1; Q3)	xxx (xxx; xxx)	xxx (xxx; xxx)	xxx (xxx; xxx)
min max	xxx to xxx	xxx to xxx	xxx to xxx
Eyes Open	xxx	xxx	xxx
1=none	xxx xx.x%	xxx xx.x%	xxx xx.x%
2=To pain	xxx xx.x%	xxx xx.x%	xxx xx.x%
3=To speech	xxx xx.x%	xxx xx.x%	xxx xx.x%
4=Spontaneously	xxx xx.x%	xxx xx.x%	xxx xx.x%
Verbal Response	xxx	xxx	xxx
1=none	xxx xx.x%	xxx xx.x%	xxx xx.x%
2=Incomprehensible sounds	xxx xx.x%	xxx xx.x%	xxx xx.x%
3=Inappropriate words	xxx xx.x%	xxx xx.x%	xxx xx.x%
4=Confused	xxx xx.x%	xxx xx.x%	xxx xx.x%
5=Orientated	xxx xx.x%	xxx xx.x%	xxx xx.x%
Motor Response	xxx	xxx	xxx

	Intensive BP lowering (N = )	Guideline-recommended BP lowering (N = )	Total (N = )
1=none	xxx xx.x%	xxx xx.x%	xxx xx.x%
2=Extension to pain	xxx xx.x%	xxx xx.x%	xxx xx.x%
3=Flexion to pain	xxx xx.x%	xxx xx.x%	xxx xx.x%
4-Withdraws	xxx xx.x%	xxx xx.x%	xxx xx.x%
5=Localises to pain	xxx xx.x%	xxx xx.x%	xxx xx.x%
6=Obey commands	xxx xx.x%	xxx xx.x%	xxx xx.x%
Time from onset to diagnostic CT	xxx	xxx	xxx
Mean (SD)	xxx.x (xxx.x)	xxx.x (xxx.x)	xxx.x (xxx.x)
Median (Q1; Q3)	xxx (xxx; xxx)	xxx (xxx; xxx)	xxx (xxx; xxx)
min max	xxx to xxx	xxx to xxx	xxx to xxx
Time from onset to diagnostic MRI	xxx	xxx	xxx
Mean (SD)	xxx.x (xxx.x)	xxx.x (xxx.x)	xxx.x (xxx.x)
Median (Q1; Q3)	xxx (xxx; xxx)	xxx (xxx; xxx)	xxx (xxx; xxx)
min max	xxx to xxx	xxx to xxx	xxx to xxx
Time from onset to groin puncture	xxx	xxx	xxx
Mean (SD)	xxx.x (xxx.x)	xxx.x (xxx.x)	xxx.x (xxx.x)
Median (Q1; Q3)	xxx (xxx; xxx)	xxx (xxx; xxx)	xxx (xxx; xxx)
min max	xxx to xxx	xxx to xxx	xxx to xxx
Time from groin puncture to recanalisation	xxx	xxx	xxx
Mean (SD)	xxx.x (xxx.x)	xxx.x (xxx.x)	xxx.x (xxx.x)
Median (Q1; Q3)	xxx (xxx; xxx)	xxx (xxx; xxx)	xxx (xxx; xxx)
min max	xxx to xxx	xxx to xxx	xxx to xxx
Time from recanalisation to randomisation	xxx	xxx	xxx
Mean (SD)	xxx.x (xxx.x)	xxx.x (xxx.x)	xxx.x (xxx.x)
Median (Q1; Q3)	xxx (xxx; xxx)	xxx (xxx; xxx)	xxx (xxx; xxx)
min max	xxx to xxx	xxx to xxx	xxx to xxx
Time from onset to randomisation	xxx	xxx	xxx
Mean (SD)	xxx.x (xxx.x)	xxx.x (xxx.x)	xxx.x (xxx.x)
Median (Q1; Q3)	xxx (xxx; xxx)	xxx (xxx; xxx)	xxx (xxx; xxx)
min max	xxx to xxx	xxx to xxx	xxx to xxx

	Intensive BP lowering (N = )	Guideline-recommended BP lowering (N = )	Total (N = )
Systolic blood pressure after recanalisation	xxx	xxx	xxx
Mean (SD)	xxx.x (xxx.x)	xxx.x (xxx.x)	xxx.x (xxx.x)
Median (Q1; Q3)	xxx (xxx; xxx)	xxx (xxx; xxx)	xxx (xxx; xxx)
min max	xxx to xxx	xxx to xxx	xxx to xxx
Diastolic blood pressure after recanalisation	xxx	xxx	xxx
Mean (SD)	xxx.x (xxx.x)	xxx.x (xxx.x)	xxx.x (xxx.x)
Median (Q1; Q3)	xxx (xxx; xxx)	xxx (xxx; xxx)	xxx (xxx; xxx)
min max	xxx to xxx	xxx to xxx	xxx to xxx
IV thrombolysis administered	xxx	xxx	xxx
yes	xxx xx.x%	xxx xx.x%	xxx xx.x%
no	xxx xx.x%	xxx xx.x%	xxx xx.x%
Brain imaging features			
CT performed	xxx xx.x%	xxx xx.x%	xxx xx.x%
MRI performed	xxx xx.x%	xxx xx.x%	xxx xx.x%
Visible early ischaemic changes	xxx xx.x%	xxx xx.x%	xxx xx.x%
Visible cerebral infarction lesion	xxx xx.x%	xxx xx.x%	xxx xx.x%
Visible cerebral infarction with mass effect	xxx xx.x%	xxx xx.x%	xxx xx.x%
Volume of infarct core (RAPID software)	xxx	xxx	xxx
Mean (SD)	xxx.x (xxx.x)	xxx.x (xxx.x)	xxx.x (xxx.x)
Median (Q1; Q3)	xxx (xxx; xxx)	xxx (xxx; xxx)	xxx (xxx; xxx)
min max	xxx to xxx	xxx to xxx	xxx to xxx
Volume of perfusion lesion			
Mean (SD)	xxx.x (xxx.x)	xxx.x (xxx.x)	xxx.x (xxx.x)
Median (Q1; Q3)	xxx (xxx; xxx)	xxx (xxx; xxx)	xxx (xxx; xxx)
min max	xxx to xxx	xxx to xxx	xxx to xxx
Mismatch volume	xxx	xxx	xxx
Mean (SD)	xxx.x (xxx.x)	xxx.x (xxx.x)	xxx.x (xxx.x)
Median (Q1; Q3)	xxx (xxx; xxx)	xxx (xxx; xxx)	xxx (xxx; xxx)
min max	xxx to xxx	xxx to xxx	xxx to xxx

	Intensive BP lowering (N = )	Guideline-recommended BP lowering (N = )	Total (N = )
Occlusion cerebral vessel site	XXX	XXX	XXX
ACA	XXX XX.X%	XXX XX.X%	XXX XX.X%
M1 MCA	XXX XX.X%	XXX XX.X%	XXX XX.X%
M2 MCA	XXX XX.X%	XXX XX.X%	XXX XX.X%
TICA	XXX XX.X%	XXX XX.X%	XXX XX.X%
Proximal ICA	XXX XX.X%	XXX XX.X%	XXX XX.X%
PCA	XXX XX.X%	XXX XX.X%	XXX XX.X%
VA	XXX XX.X%	XXX XX.X%	XXX XX.X%
BA	XXX XX.X%	XXX XX.X%	XXX XX.X%
eTICI score before EVT	XXX	XXX	XXX
0	XXX XX.X%	XXX XX.X%	XXX XX.X%
I	XXX XX.X%	XXX XX.X%	XXX XX.X%
IIa	XXX XX.X%	XXX XX.X%	XXX XX.X%
IIb	XXX XX.X%	XXX XX.X%	XXX XX.X%
IIc	XXX XX.X%	XXX XX.X%	XXX XX.X%
III	XXX XX.X%	XXX XX.X%	XXX XX.X%
EVT details			
Anesthesia used	XXX XX.X%	XXX XX.X%	XXX XX.X%
General	XXX XX.X%	XXX XX.X%	XXX XX.X%
Conscious sedation	XXX XX.X%	XXX XX.X%	XXX XX.X%
Type of device used			
Stent retriever	XXX XX.X%	XXX XX.X%	XXX XX.X%
Aspiration catheter	XXX XX.X%	XXX XX.X%	XXX XX.X%
Balloon guide catheter	XXX XX.X%	XXX XX.X%	XXX XX.X%
Angioplasty	XXX XX.X%	XXX XX.X%	XXX XX.X%
Other	XXX XX.X%	XXX XX.X%	XXX XX.X%
Use of antithrombotic drugs	XXX	XXX	XXX
Heparin	XXX XX.X%	XXX XX.X%	XXX XX.X%
Mean dose	xxx.x (xxx.x)	xxx.x (xxx.x)	xxx.x (xxx.x)
GPIIb/IIIa inhibitor	XXX XX.X%	XXX XX.X%	XXX XX.X%
Tirofiban	XXX XX.X%	XXX XX.X%	XXX XX.X%

	Intensive BP lowering (N = )	Guideline-recommended BP lowering (N = )	Total (N = )
Other	XXX XX.X%	XXX XX.X%	XXX XX.X%
Use of intra-arterial thrombolysis	XXX XX.X%	XXX XX.X%	XXX XX.X%
Number of retrieval attempts/passes			
1	XXX XX.X%	XXX XX.X%	XXX XX.X%
2	XXX XX.X%	XXX XX.X%	XXX XX.X%
3	XXX XX.X%	XXX XX.X%	XXX XX.X%
>3	XXX XX.X%	XXX XX.X%	XXX XX.X%
eTICI score after EVT	XXX	XXX	XXX
0	XXX XX.X%	XXX XX.X%	XXX XX.X%
I	XXX XX.X%	XXX XX.X%	XXX XX.X%
IIa	XXX XX.X%	XXX XX.X%	XXX XX.X%
IIb	XXX XX.X%	XXX XX.X%	XXX XX.X%
IIc	XXX XX.X%	XXX XX.X%	XXX XX.X%
III	XXX XX.X%	XXX XX.X%	XXX XX.X%
Final diagnosis	XXX	XXX	XXX
Intracranial atherosclerosis	XXX XX.X%	XXX XX.X%	XXX XX.X%
External atherosclerosis	XXX XX.X%	XXX XX.X%	XXX XX.X%
Cardioembolism (AF-related)	XXX XX.X%	XXX XX.X%	XXX XX.X%
Cardioembolism (valve or myocardium)	XXX XX.X%	XXX XX.X%	XXX XX.X%
Stroke due to dissection	XXX XX.X%	XXX XX.X%	XXX XX.X%
Stroke of uncertain aetiology	XXX XX.X%	XXX XX.X%	XXX XX.X%

